17.2.6 Vasopressor requirement

The vasopressor requirement will be compared using a generalised linear mixed model (i.e. a logistic regression model with a random effect of patient). An odds ratio will be reported comparing the use over d2-d5, as well as the timepoint specific use. Study site will be added in the model. Note that the model will be fit on information from d1-d5. Note that the mean duration of vasopressor requirement (i.e. in the period d2-d5) can be derived directly from this model as the sum of the daily probabilities. Vasopressor requirement is an ordinal scale (4 levels starting with 'no') and results will be reported from separate models using the three possible cutpoints (for example 'no' versus 'yes').

For discharged patients, no vasopressor requirement is assumed. For deceased patients, requirement and dosage are put on missing from that day on (in case information was available on the day of death, the information is considered missing from the day after death on).

17.2.7 Renal replacement therapy

The probability of renal replacement therapy (RRT) will be compared using a generalised linear mixed model (i.e. a logistic regression model with a random effect of patient). An odds ratio will be reported comparing the 'mean probability' over d2-d5. Given the expected low number of events, for the timepoint specific RRT only descriptives will be reported. RRT is put on zero when the patient is discharged. When a subject is deceased, the value is considered missing from that day on (in case RRT information was available on the day of death, the information is considered missing from the day after death on). Note that the model will be fit on daily information from d1-d5 and that the mean duration of RRT (i.e. in the period d2-d5) can be derived directly from this model as the sum of the daily probabilities.

17.2.8 Mechanical ventilation

The probability of mechanical ventilation (MV) will be compared using a generalised linear mixed model (i.e. a logistic regression model with a random effect of patient). An odds ratio will be reported for the comparison of the 'mean probability' over d2-d5, and for the day-specific comparisons. MV is put on zero when patient is discharged. When a subject is deceased, the value is considered missing from that day on (in case MV information was available on the day of death, the information is considered missing from the day after death on). Note that the model will be fit on daily information from d1-d5 and the mean duration of MV (i.e. in the period d2-d5) can be derived directly from this model as the sum of the daily probabilities.

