The required sample size is calculated to detect with at least 80% power a difference in average post-baseline patient SOFA score (calculated over days 2 to 5), based on a constrained longitudinal data analysis model with alpha set at 0.05 (Liang and Zeger, 2000). The power is calculated using an approach presented by Stroup (Stroup, 1999). In the cLDA, both the baseline and post-baseline value are modeled as dependent variables, as opposed to a (longitudinal) ANCOVA model in which the baseline value is included as a covariate. Although the baseline measure is included in the response vector in cLDA, the true baseline means are constrained to be the same for different treatment groups due to randomization, and this analysis provides an adjustment for the observed baseline difference in estimating the treatment effects. Since the randomization is performed within center, considering center as an effect in the analysis has no impact on the sample size. Patients who die within the time period of 5 days receive the worst outcome (highest SOFA score) starting at the day of death. Based on the cLDA model, 126 patients per group (252 patients in total) are needed to detect with at least 80% power a difference between the control and intervention group of 1 in average post- baseline SOFA score. A standard deviation of the SOFA score equal to 3.5 and a correlation between the time points equal to 0.5 was assumed. These were conservative estimates, derived from reported information in two studies (Fowler et al, 2019; Fujii et al. 2020). 2.5%, 5%, 10% and 15% missing values are assumed on d2, d3, d4 and d5, respectively (combination of dropout and mortality). However, the sample size will be increased to 150 patients per group to anticipate a larger variability due to the imputation of one or more maximal SOFA scores for deceased patients.

7 Analysis Populations

The following analysis sets will be of interest:

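### The summed daily probabilities in SAP sections 17.2.6 to 17.2.8 are not the mean duration of support: they count predicted support on days after death

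*SAP*

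**What the plan says.** Section 4.2.2 lists vasopressor duration, RRT duration and ventilator days among the secondary outcomes. Sections 17.2.6, 17.2.7 and 17.2.8 analyse all three in the same way, with a logistic model that has a random patient effect and is fitted to d1-d5.

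- **Discharge.** For MV, "MV is put on zero when patient is discharged"; for RRT, "RRT is put on zero when the patient is discharged". Section 17.2.6 likewise assumes no vasopressor need after discharge.
- **Death.** For MV and RRT, "When a subject is deceased, the value is considered missing from that day on". For vasopressors, "For deceased patients, requirement and dosage are put on missing from that day on". All three sections add an exception, which for MV reads "in case MV information was available on the day of death, the information is considered missing from the day after death on".
- **Duration.** Section 17.2.8 states that "the mean duration of MV (i.e. in the period d2-d5) can be derived directly from this model as the sum of the daily probabilities". Sections 17.2.6 and 17.2.7 say the same for vasopressors and RRT. No section weights the sum by survival.

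Section 9 handles missing longitudinal data by direct likelihood under missing at random (MAR). Death is treated differently elsewhere. For SOFA, section 6 says "Patients who die within the time period of 5 days receive the worst outcome (highest SOFA score) starting at the day of death", and section 9 sets that score at 24. Death is a competing risk for length of stay (17.2.1, 17.2.2) and return to work (17.2.12).

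**The concern.** A patient ventilated on d1 and d2 who dies on d3 contributes no zeros for d4 and d5. The model fills the gap implicitly: the high patient effect implied by d1 and d2 carries forward, so the population probabilities for d4 and d5 include predicted ventilation for someone who is dead. Adding those probabilities over d2-d5 gives the expected support days in a cohort without deaths. That is not the number of days of support given, which is the ordinary meaning of the durations named in section 4.2.2. Nor does it count death as unfavourable. The SAP does not say that the figure is hypothetical.

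Two things are at stake. A figure published as mean ventilator days could be noticeably larger than the days delivered. And if early mortality differed between arms, the sum would show neither the resulting difference in days given nor the difference in days alive and free of support.

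**Working it through.** The SAP gives no duration figure, so there is nothing to reproduce. The check is whether the sum equals the days of support given.

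**Identity.** Let Y_t be support on day t and A_t = 1 if the patient is alive.

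- Days given = sum over t = 2..5 of P(A_t = 1, Y_t = 1).
- SAP sum = sum over t = 2..5 of the model's P(Y_t = 1), without A_t.
- The difference is the model's predicted support on days after death. It is zero only if nobody dies or those who die have no predicted support.

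**Simulation.** From the SAP: the random-intercept logistic model, d1-d5, and missing values after death. Assumed, because the SAP gives no values: daily support probability 0.2, random-effect SD 3 on the logit scale, no discharge, and a daily death risk set by the previous day's support (0 to 20% on support, 0 to 2% off), which satisfies MAR. There were 200,000 patients per scenario. The model was fitted by maximum likelihood with 41-point Gauss-Hermite quadrature, and the probabilities were averaged over the patient effect before summing. The first missing day can be read as a day of death with nothing recorded, or as the day after a recorded day of death.

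| Dead by d5 | SAP sum | Days given | Excess | Sum of daily proportions among those alive | Days alive and free |
|---|---|---|---|---|---|
| 0% | 0.793 | 0.793 | 0 | 0.793 | 3.207 |
| 6.8% | 0.799 | 0.734 | 0.065 (0.799/0.734 = 1.09) | 0.767 | 3.093 |
| 10.4% | 0.799 | 0.679 | 0.120 (0.799/0.679 = 1.18) | 0.727 | 3.053 |
| 19.2% | 0.796 | 0.579 | 0.217 (0.796/0.579 = 1.37) | 0.659 | 2.917 |

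The SAP sum stays at its no-death value while the days given fall.

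**Other inputs.**
- Probability 0.3, SD 3: the sum is 1.20, 1.19 and 1.20 at 8.4%, 13.5% and 24.7% dead, against 1.09, 1.00 and 0.84 days given. The excess is about 10%, 19% and 43%.
- Probability 0.2, SD 2: the sum is 0.80 throughout, against 0.74, 0.70 and 0.61 at 7.0%, 10.4% and 19.7% dead. The excess is about 8%, 14% and 31%.
- A separate simulation with SD 4 and 40,000 patients per scenario gave 0.83 against 0.76, 0.69 and 0.63 at 6%, 10% and 15% dead. The excess is about 9%, 20% and 32%.

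**Bound from the SAP's planning figures.** Section 6 assumes 2.5%, 5%, 10% and 15% missing on d2 to d5, dropout and mortality combined. That is 0.025 + 0.05 + 0.10 + 0.15 = 0.325 missing days per patient. If all were deaths, with predicted support probability 0.5 to 0.9 (both assumptions), the sum would gain 0.325 × 0.5 = 0.16 to 0.325 × 0.9 = 0.29 days per patient. Over 150 patients per arm that is about 24 to 44 days.

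**Averaging.** The SAP does not say whether the probabilities are averaged over the patient effect. Evaluated at a patient effect of zero, the sum in the tabulated setting is about 0.20 instead of 0.80. This is a separate ambiguity; the excess shown above is present even with correct averaging.

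**The case against.** The strongest reply is that the death rule is deliberate and defensible. No support after live discharge is close to fact, whereas support status after death is undefined. Sections 17.2.9 to 17.2.11 also set values after death to missing. An odds ratio for support given survival is a recognisable estimand. Mortality at 28 days is its own outcome (17.2.5), deaths to day 5 are tabulated by arm (section 15), and the formal comparison is the odds ratio, with duration mentioned only in a note. Days given would be a poor target by themselves, since they fall as deaths rise and so favour the arm with more deaths.

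Most of this stands. It protects the odds ratio but not the sentence about duration. Calling the sum conditional on survival would not rescue it either: in the table, the daily proportions among those alive add up to 0.767, 0.727 and 0.659, not 0.80.

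A reader might infer that the plan biases the comparison between arms, or favours the arm with more deaths. The documents do not support that. An excess common to both arms leaves their difference unchanged, and nothing in the SAP suggests that early death will differ. If it did, the effect could be small: in the SD 4 simulation, 6% against 10% dead moves days alive and free from 3.09 to 3.03. With an assumed SD of 1.2 to 1.6 and 150 per arm, the standard error is SD × √(2/150), about 0.14 to 0.18, so 0.06 days is under half a standard error.

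A reader might also infer that scoring death as worst for SOFA obliges the support outcomes to do the same. It does not. Separate or composite reporting of death is a choice, and replacing the planned odds ratios with a composite would be a trade-off, not a correction.

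**Conclusion.** The point holds as a wrongly stated derivation of named secondary outcomes. Without survival weighting, the sum is the support expected if nobody died before d5, and it exceeds the support given whenever patients on support die early. In the tabulated setting the excess is 0.065 to 0.217 days per patient. Across the settings tried it runs from about 8% to 43%, the top figure at 24.7% mortality.

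These sizes rest on assumed support rates, patient heterogeneity and death risks, on death concentrated among patients on support, and on MAR. The section 6 figures do not separate death from dropout, and section 17.2.7 itself expects few RRT events, so for RRT the absolute excess may be slight. That death carries no direct penalty does not mean deaths cannot move the estimate; they can if MAR or the model fails. Section 13 treats the secondary analyses as exploratory, and the primary SOFA conclusion is untouched.

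**What to change.** In sections 17.2.6, 17.2.7 and 17.2.8:

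1. Keep the mixed-model odds ratios as planned and label them as support while alive, that is, conditional on survival.
2. Remove the statement that the unweighted sum is the mean duration.
3. Report observed support days over d2-d5 by arm, descriptively and always beside the deaths to day 5 from section 15, because days given alone flatter an arm with more deaths.
4. Add, as a supplementary analysis, a site-adjusted comparison of days alive and free of each support over d2-d5 (0 to 4). Days from death on count as not free; days after live discharge count as free, which keeps the SAP's discharge rule. For vasopressors, the no-versus-yes cut that section 17.2.6 already uses will serve.

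The cost is a documented SAP change and a few lines of code, using support, discharge and death data the plan already needs. The downside is one more composite that also reflects early deaths, so it should be read beside mortality and not in place of the planned outcomes.

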17.2.9 Dose and need of steroids

The daily dose of steroids given will be compared between both groups using a multivariate normal model for longitudinal measurements, with the Aikake criterion to select the covariance matrix. The mean dosage over d2-d5 will be compared, as well as the timepoint specific dosages. Study site will be added in the model. Note that the model will be fit on information from all patients in the period d1-d5. For discharged, lost-to-FU and deceased patients, the dose will be put on missing.

The need of steroids (MV) will be compared using a generalised linear mixed model (i.e. a logistic regression model with a random effect of patient) with site added as a fixed effect. An odds ratio will be reported for the comparison of the 'mean probability' over d2-d5, and for the day-specific comparisons.

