4.2.2 Secondary Outcomes

The following secondary outcomes will be of interest:

- Day-specific SOFA score (day 2-5)
- Maximum SOFA score (day 2-5)
- 28-day mortality
- Length of hospital stay
- Length of ICU stay
- Vasopressor requirement: total duration and dosage
- RRT duration and need
- Ventilator days
- Total dose of steroids given
- Lab values :
 - Creatinine, CRP on d2-d5
 - Procalcitonin on d4
- Quality of life (EQ-5D-5L)
- Time to return to work (if applicable)

5 Sequence of Planned Analyses

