8.3 Centre Effect

All statistical analyses of the outcomes of interest will be adjusted for study site. When applying the adjustment, the small site ULB Erasme (3 patients in the FAS) will be combined with UZ Brussels (Jette), as decided during the Blind review meeting (September 25, 2023).

9 Methods for Missing Data

In the statistical analyses of the longitudinally measured outcomes the presence of missing values is handled using a direct likelihood approach to fit the multivariate models. As such, the analysis is valid under the missing at random assumption (MAR).

Handling missing data for the SOFA score

In some settings, the following rules for single imputation will be used to handle missing SOFA scores or missing components for the calculation of the SOFA score.

- Patients who die within the time period of 5 days receive the worst outcome (highest SOFA score being equal to 24) starting at the day of death (even if a SOFA score is available at the day of death).
- SOFA scores are considered missing after the day of discharge
- If the patient's status does not require a lab analysis (due to good condition of the patient), missing data occur as per protocol. In this case the best possible score will be used for the SOFA score calculation (i.e. 0 points for bilirubin, blood platelets and creatinin) in the daily follow-up.
- If however a lab analysis was not ordered but was required as per protocol, the SOFA score of that day will be considered as missing.
- If a lab analysis was required, but one of the three lab values needed in the SOFA score was missing, the previous lab value was used for the calculation of the SOFA score. This was deemed appropriate, since it can be assumed that the specific lab parameter was not ordered that day because the function was considered stable. In rare cases where this happened at d1, the value of d2 will be used for the calculation of the SOFA score.

Frequency tables will be reported for the various settings where above imputation rules were applied.

For the analysis of the maximal SOFA score a multiple imputation approach will be used (cfr infra for details of the imputation model).

10 Data Transformations

An inverse hyperbolic sign transformation will be applied in the analysis of the (maximal) SOFA to obtain a more symmetric distribution of the model residuals. Analyses on untransformed scores will be reported as sensitivity analyses.

11 Multicenter Study

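### Steroid dose is set to missing after live discharge while vasopressors, RRT and ventilation are set to zero, so the d2-d5 mean does not estimate the listed total dose given

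*SAP*

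**What the plan says.** Section 4.2.2 lists the endpoint as "Total dose of steroids given". Section 17.2.9 analyses daily dose with a multivariate normal longitudinal model. On the contrast it says "The mean dosage over d2-d5 will be compared, as well as the timepoint specific dosages", and on the data "Note that the model will be fit on information from all patients in the period d1-d5". Its rule for patients who leave is "For discharged, lost-to-FU and deceased patients, the dose will be put on missing".

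The three preceding sections treat live discharge differently:

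- 17.2.6: "For discharged patients, no vasopressor requirement is assumed".
- 17.2.7: "RRT is put on zero when the patient is discharged".
- 17.2.8: "MV is put on zero when patient is discharged".

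In those three sections a missing value is prescribed after death, not after discharge. Section 9 says how missing daily values are then treated: "In the statistical analyses of the longitudinally measured outcomes the presence of missing values is handled using a direct likelihood approach", valid under missing at random. The second model in 17.2.9, for need of steroids, has no rule for discharge. The SAP gives no reason for treating steroids differently.

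**The concern.** The same event, going home alive, counts as a known zero for three daily treatment outcomes and as an unknown value for the fourth. In 17.2.9 it falls in the same class as loss to follow-up. A likelihood model with missing days estimates the arm mean as if those days had been observed in hospital, conditional on each patient's earlier doses. The result describes a trial in which nobody is discharged.

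Two groups raise the fitted mean above the dose given in hospital. Discharged patients who had been on steroids have their in-hospital level carried forward. Late new starts among patients still in hospital also feed into the predictions for those who have left. Earlier discharge is one route by which a treatment could lower the total dose, and this rule takes it out of the comparison. Section 15 tabulates discharges up to day 5, so the situation is expected to occur.

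**Working it through.** The SAP states no steroid dose, share of users or discharge rate, so it has no figure to reproduce. All inputs below are assumptions chosen to show direction and range.

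**Illustration A: discharge unrelated to steroid use.** Assume 30% of patients are users at 200 units/day, so the control in-hospital mean is 0.30 × 200 = 60. Let r be the in-hospital dose ratio, intervention to control. Assume cumulative discharge on d2, d3, d4, d5 of 2, 6, 12, 20% (control) and 5, 14, 26, 40% (intervention).

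- Average share of d2-d5 spent in hospital: control (0.98 + 0.94 + 0.88 + 0.80)/4 = 3.60/4 = 0.900; intervention (0.95 + 0.86 + 0.74 + 0.60)/4 = 3.15/4 = 0.7875.
- Zero after discharge: control mean = 60 × 0.900 = 54.0; intervention mean = 60 × r × 0.7875 = 47.25r.
- Missing after discharge: control mean = 60; intervention mean = 60r.

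Differences are intervention minus control. The simulated columns come from fitting the multivariate normal model by maximum likelihood to 30,000 patients per arm, with unstructured covariance and no site term.

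| r | Zero rule, by formula | Zero rule, simulated | Missing rule, by formula | Missing rule, simulated |
|---|---|---|---|---|
| 1.00 | 47.25 - 54.0 = -6.75 | -6.8 | 0.0 | 0.0 |
| 1.05 | 49.6 - 54.0 = -4.4 | -4.5 | +3.0 | +3.0 |
| 1.10 | 52.0 - 54.0 = -2.0 | -1.9 | +6.0 | +6.1 |

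The signs differ only when r lies between 1 and the ratio of in-hospital time, 3.60/3.15 = 1.14. With discharge of 3, 8, 15, 25% v 4, 10, 20, 30%, the upper limit is 3.49/3.36 = 1.04. At r = 1.05 the two rules then agree in sign (+0.7 v +3.1).

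**Varying the assumptions** (zero rule first, missing rule second):

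- Users leave at half the non-user rate, 20% v 40% discharged: r = 1.05 gives -1.3 v +3.3; r = 1.10 gives +1.4 v +6.4.
- Equal discharge, 30% per arm: r = 0.90 gives -4.9 v -5.9; r = 1.10 gives +5.1 v +6.2. The sign holds. The level does not: in the r = 0.90 run the control mean is 50.4 v 60.1, a ratio of 1.19.
- Almost no user discharged by d5: -3.1 v -3.1 in one setting and +5.8 v +6.7 in another.

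In these runs, on days after discharge, the model implies about 190 to 220 units for former users and close to 0 (-0.3 to 6) for non-users.

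**Illustration B: only patients off steroids are discharged.** Assume 25% are on 200 units/day at d1, 15% of users stop and 4% of non-users start each day, and from d3 a daily discharge of 20% v 35% among patients off steroids. About 38% v 57% are discharged by d5.

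- Discharge follows the same day's dose, so missing at random fails. The in-hospital means are 45.8 v 45.0 (difference about -0.75). The missing rule gives about 50.7 v 53.9 (+3.2). The sign reverses.
- Discharge follows the previous day's status, so missing at random holds. The means 44.5 v 42.8 (-1.7) become 47.0 v 46.8 (-0.2). The difference is erased, not reversed.

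For scale, at 150 per arm the standard error of the arm difference in illustration B is about 8.7 units. Hence -0.75/8.7 is 0.09 and 3.2/8.7 is 0.37 standard errors.

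**The case against.** **Missing after discharge is not unique to steroids.** Section 9 makes SOFA scores missing after discharge, and section 17.2.10 limits fluid balance to ICU days. The zero rule appears only in the logistic models. This is true, but a SOFA score still exists unmeasured at home, and the fluid outcome is explicitly restricted to ICU days. Steroid dose is analysed in all patients and listed as an amount given, and the amount given in hospital after discharge is known.

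**Zero is itself an assumption.** A patient may go home on steroids, and the SAP does not say whether that is recorded. This stands. Zero is exact only for dose given in hospital, so the outcome has to be defined before the rule can be called right.

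**The effect may be negligible.** A reader might infer that the model gives steroids to every discharged patient, or that the comparison will come out reversed. The document supports neither. Non-users are predicted near zero. Reversal needs discharge timing that differs between arms, together with a small opposite difference in in-hospital dose or discharge that follows the same day's dose. All rates above are assumed, and the shifts in illustration B are well below one standard error at the planned size.

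**It is one of many unadjusted secondary outcomes.** Section 13 calls these analyses exploratory. That limits the weight of the point, although section 17 still tests the outcome at two-sided 0.05, and section 17.2 does so in both analysis sets.

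**Conclusion.** The inconsistency between 17.2.9 and 17.2.6-17.2.8 is on the page and unexplained. Combined with section 9, the missing rule makes the fitted d2-d5 mean the dose expected had nobody been discharged, which differs from the endpoint in 4.2.2.

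The fitted mean tends to exceed the dose given in hospital. When arms differ in discharge timing, a small arm difference can be attenuated, erased or, in some settings, reversed. With equal discharge the sign is kept. The effect is small if almost no steroid user leaves early and discharge does not follow the same-day dose. The actual size cannot be derived, because the SAP gives neither doses nor discharge rates.

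Sign reversal is a possibility under stated assumptions, not a predicted result. The point concerns one secondary, exploratory outcome and leaves the primary analysis and the sample size untouched.

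**What to change.** In section 17.2.9:

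1. State that the outcome is the steroid dose given in hospital over d2-d5.
2. Set dose and need to 0 on days after live discharge, in line with 17.2.6-17.2.8.
3. Keep missing for loss to follow-up and, as now, for death.
4. Apply the same rule to the need-of-steroids model, which has no discharge rule at present.

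The cost is one or two sentences and no new data. The downside is that steroids taken at home are not counted. If the sponsor wants dose wherever it is taken, neither the zero rule nor the present missing rule measures it, and the SAP should say so.
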